8.1.9. Safety Analyses

Safety data will be summarized for the Safety Population. All safety presentations will be descriptive, and all summaries will be displayed by treatment arm.

8.1.9.1. Extent of Exposure

The extent of exposure to study drug will be summarized by the number of doses taken, number of missed doses, and compliance with IP administration. Investigational product noncompliance for a patient is defined as taking less than 80% or more than 120% of IP during the treatment period (Day 1 through EOT).

8.1.9.2. Adverse Events

All AEs occurring during the study will be recorded and classified using terminology from MedDRA. A treatment-emergent AE (TEAE) is defined as any AE that has an onset on or after the first dose of IP or any preexisting condition that has worsened on or after the first dose of IP.

The incidence of TEAEs (number and percent of patients reporting the AE at least once during the study), SAEs, AEs related to study treatment, SAEs related to treatment, and AEs leading to study discontinuation will be summarized by treatment. Treatment-emergent AEs will also be summarized by severity and relationship to IP. When summarizing TEAEs by severity or relationship to IP, each patient will only be counted once within a system organ class or preferred term using the event with the greatest severity or causality, respectively, within each category.

A listing of patients who prematurely discontinue from the study due to AEs will be provided as well as a list of patients who reported SAEs.

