Clinic study visits will occur on Days 1, 7, 14, 21, and 28 (end-of-treatment [EOT] visit) (± 1 day). Patients in the double-blinded Treatment Arms 1, 2, and 3 will be evaluated in a follow-up visit on Day 56 (± 2 days) (28 days after EOT). Patients in the open-label SOC Treatment Arm 4 will be discontinued from the study after the EOT visit.

Baseline symptoms will include chronic cough, fatigue, frequent throat clearing, dyspnea, hemoptysis, excessive mucus (sputum) production, fever, night sweats, loss of appetite, unintended weight loss, wheezing, and chest pain. A multi-dimensional patient-reported outcome (PRO) (see [Appendix 3](#)) instrument assessing severity and changes in these baseline symptoms

will be administered at clinic visits on Days 1, 7, 14, 21, and 28 in all arms and Day 56 in Treatment Arms 1, 2, and 3.

Patient-collected pooled expectorated sputum will be collected on Days –1, 6, 13, 20, and 27 (i.e., the day before clinical study visits over an approximate 24-hour [h] period) for all patients and, for patients in Treatment Arms 1, 2, and 3, on Day 55 (i.e., the day before the follow-up visit on Day 56). In all cases, the patient-collected sputum will be collected on the day before the actual clinic visit. Sputum will also be collected at each clinic visit using a standard induction protocol.

[figure not shown]
Patients in Treatment Arms 1, 2, and 3 will participate in the collection of blood samples for PK analysis as follows:

- At least 3 selected qualifying sites will enroll a total of at least 18 patients (at least 6 per treatment arm) for intensive PK evaluation. On Days 1 and 28, blood samples for intense PK will be collected at pre-dose and post-dose: 1 h, 2 h, 4 h, 8 h, 12 h, and 24 h. On Days 7, 14, and 21, blood samples will be obtained at: pre-dose, 1 h post-dose, and just before discharge from the clinic. The acceptable windows for PK collection are specified in the Schedule of Assessments ([Table 2](#)).
- At all remaining, samples will be collected for sparse PK evaluation, on Days 1, 7, 14, 21, and 28. Blood samples will be obtained at pre-dose, 1 h post-dose, and just before discharge from the clinic.
- Patients randomized to the SOC arm will not participate in PK collection.

Actual dates and times of blood samples as well as dates and times of study drug administration will be recorded. Please refer to the Schedule of Assessments ([Table 2](#)) for allowable windows.

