3.2. Study Duration

Patients will be screened within 42 days prior to the first dose of study drug. All patients will be treated for 28 days. Patients in Treatment Arms 1, 2, and 3, only, will have a follow-up visit 28 days after the completion of therapy. The maximum duration of participation for each patient will be approximately 98 days (including a 42-day screening period, 28-day treatment period, and 28-day follow-up period) for Treatment Arms 1, 2, and 3, and approximately 70 days (including a 42-day screening period and 28-day treatment period) for Treatment Arm 4 SOC recipients.

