3.3.4. Withdrawal from Study

A patient will be considered to have completed the study when he or she completes the EOT visit for patients in Treatment Arm 4 and the follow-up visit on Day 56 (± 2 days) for patients in Treatment Arms 1, 2, and 3.

Patients may withdraw from the study or be withdrawn at the request of the Investigator or Sponsor at any time. Examples of reasons for study withdrawal include the following:

- The patient withdraws consent or requests withdrawal from the study for any reason
- The patient is lost to follow-up
- The patient fails to comply with protocol requirements or study-related procedures
- The Investigator determines that it is in the best interest of the patient to withdraw from the study protocol for reasons other than an adverse event (AE)
- The study is terminated or temporarily suspended by the Sponsor or a regulatory authority for any reason including, but not limited to, study drug-related unexpected life-threatening serious AEs (SAEs) detected during safety monitoring (e.g., torsade de pointes or other ventricular arrhythmias), and 2 or more of the same drug-related (possible or probable) treatment-emergent SAE

Patients who wish to withdraw completely from this clinical study during the treatment period should be encouraged to undergo the EOT safety and efficacy assessments at the time of withdrawal as shown in the Schedule of Assessments (Table 2). For a patient who agrees to complete the EOT visit, blood draws for PK will not be conducted. In addition, for women of child-bearing potential a pregnancy test should be conducted at this visit. Once a patient withdraws consent, no further data will be collected.

A patient is considered lost to follow-up if he or she fails to return to the study clinic for scheduled visits and is unable to be contacted by the study site. The site must attempt to contact the patient at least twice by phone or letter, and, if no response is obtained from the patient, a certified letter will be sent requesting that the patient contact the Investigator and asking that they return any unused IP and return to the site for a final evaluation. Documentation of these efforts to contact the patient must be recorded in the patient's study file.

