8.1.9.3. Concomitant Medications

Concomitant medication verbatim terms in the eCRFs will be mapped to Anatomical/Therapeutic/Chemical (ATC) class and Preferred Names using WHODrug Global.

Concomitant medications will be summarized by ATC class and preferred name. These summaries will present the number and percentage of patients using each medication. Patients may have more than 1 medication per ATC class and preferred name. At each level of summarization, a patient will be counted only once if he/she reported 1 or more medications at that level.

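### TEAE percentages cover about 56 days in Arms 1-3 but about 28 days in SOC, so the SOC column reads low if any first events start after EOT

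*Combined protocol and SAP*

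**What the plan says.** Section 8.1.9.2 opens the event window without closing it: "A treatment-emergent AE (TEAE) is defined as any AE that has an onset on or after the first dose of IP", or a pre-existing condition that worsens from then on. The summary measure is "The incidence of TEAEs (number and percent of patients reporting the AE at least once during the study". Serious events, related events and events leading to discontinuation are listed in the same sentence. For medications, Section 8.1.9.3 says: "These summaries will present the number and percentage of patients using each medication". Section 4.7.2 defines concomitant treatment from the first dose and gives no closing date. Section 5.4 has adverse events and medications reviewed at every study visit, with events recorded until the patient's last study event.

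Follow-up differs by arm. Section 3.2: "Patients in Treatment Arms 1, 2, and 3, only, will have a follow-up visit 28 days after the completion of therapy". Section 3.1: "Patients in the open-label SOC Treatment Arm 4 will be discontinued from the study after the EOT visit". Section 3.3.4 confirms that this is completion for Arm 4 and not early termination: "A patient will be considered to have completed the study when he or she completes the EOT visit for patients in Treatment Arm 4". Section 6.6.3 adds that investigators need not look for events in former patients.

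Section 8.1.9 puts all safety summaries side by side by arm. Section 8.1.9.1 describes exposure only by doses taken, doses missed and compliance. The supplied text gives neither a common cut-off nor an exposure-adjusted rate. Section 8 promises a detailed SAP before database lock, and that SAP is not in the supplied text.

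**The concern.** A crude percentage of patients with at least one event can only stay level or rise as observation time grows. An Arm 1-3 patient whose first headache starts on Day 40 enters the numerator. An Arm 4 patient with the same headache has already left the study and does not. The difference can therefore run in only one direction: it lowers the SOC column relative to the other three.

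Safety and tolerability of SPR720 is the secondary objective, and SOC is a named comparator in the same tables. Someone reading across a row could take a difference in observation time for a difference in tolerability.

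Medications have one extra route. Inclusion criterion 7 (Section 3.3.1) requires patients to be ready to start or restart treatment within 3 months. Any such treatment begun between EOT and Day 56 would be tabulated as a concomitant medication in Arms 1-3 only. The protocol does not say how often that is expected.

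**Working it through.** **1. The plan's own durations (Section 3.2).** Arms 1-3: 42 + 28 + 28 = 98 days. Arm 4: 42 + 28 = 70 days. Both reproduce the stated figures.

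**2. Time after first dose.** Subtract the 42 screening days: 98 - 42 = 56 days and 70 - 42 = 28 days, a ratio of 2. The Day 28 visit window of 1 day either way gives 27 to 29 days in Arm 4. With follow-up 28 days (2 days either way) after EOT, as in the footnotes to Table 2, Arms 1-3 run from 27 + 26 = 53 to 29 + 30 = 59 days. The windows never overlap.

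**3. Arm sizes (Section 3.1).** 72 patients at sparse-PK sites are randomized 5:5:5:4, plus 6 per blinded arm at intense-PK sites.
- Arms 1-3: 72 × 5/19 + 6 = 24.9 each.
- Arm 4: 72 × 4/19 = 15.2.
- Total: 3 × 24.947 + 15.158 = 90, as planned.

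**4. What the documents fix about size.** One extra patient among about 25 is 100/25 = 4 points. In Arm 4, no patient who has completed can be added after EOT. With no first events after EOT, the difference is 0.

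**5. Illustration under assumed rates.** Neither input below is in the protocol. Let p be the true 28-day incidence, equal in all arms. Let f be the ratio of the hazard in follow-up to the hazard on treatment. Then SOC shows p, and a blinded arm shows 1 - (1 - p)^(1+f). For example, p = 20% and f = 0.5 gives 1 - 0.8^1.5 = 28.4%, a gap of 8.4 points.

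| True 28-day incidence (SOC column) | Blinded arm, f = 0.25 | f = 0.5 | f = 1 | Gap in points (f = 0.25 / 0.5 / 1) |
|---|---|---|---|---|
| 5% | 6.2% | 7.4% | 9.8% | 1.2 / 2.4 / 4.8 |
| 10% | 12.3% | 14.6% | 19.0% | 2.3 / 4.6 / 9.0 |
| 20% | 24.3% | 28.4% | 36.0% | 4.3 / 8.4 / 16.0 |
| 40% | 47.2% | 53.5% | 64.0% | 7.2 / 13.5 / 24.0 |
| 50% | 58.0% | 64.6% | 75.0% | 8.0 / 14.6 / 25.0 |
| 70% | 77.8% | 83.6% | 91.0% | 7.8 / 13.6 / 21.0 |
| 90% | 94.4% | 96.8% | 99.0% | 4.4 / 6.8 / 9.0 |

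At f = 0 every gap is 0. The gap is small for rare terms, largest in the middle of the range, and smaller again when nearly everyone has an event. An any-event row is therefore not automatically the worst affected.

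**6. Against chance.** With 25 v 15 patients and equal true risk, take an apparent SPR720 excess of at least 20 points (my threshold, not the protocol's). Its binomial probability at f = 0 / 0.25 / 0.5 is:
- p = 10%: 0.024 / 0.049 / 0.085
- p = 40%: 0.114 / 0.227 / 0.363
- p = 90%: 0.031 / 0.068 / 0.105

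At p = 5% the figure depends on ties, because 5/25 v 0/15 is exactly 20 points. For f = 0.5 it is 0.0164 with ties counted and 0.0046 without. No weight should rest on the low-incidence values.

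**7. What is not affected.** Arms 1, 2 and 3 share one window, so SPR720 v placebo stands. Laboratory, ECG and vital-sign summaries by visit compare like days.

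**The case against.** The strongest reply is that the plan intends no safety contrast with SOC. The objective concerns SPR720, its blinded control has the same window, no hypothesis is planned (Section 8.1.4), and every safety table is descriptive. As a count of what happened while patients were in the study, each column is correct. The unequal follow-up is stated openly, onset dates are collected (Section 6), and the SAP could still set a common window. SOC is also open label, chosen by the investigator and not assigned at intense-PK sites (Section 4.3), so aligning the windows would not make it a clean comparator.

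Most of that stands, and it limits the weight of the point. It does not remove the point. The tables set SOC beside the other arms, descriptive percentages are what the study will report on safety, and observation time is the one source of non-comparability here that can be removed with data already planned.

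Two details also need care. The words about occurrence during the study are attached to TEAEs, so extending them to serious and related events is inference. Section 8.1.9.3 states no window, so the medication point is inferred from Sections 4.7.2 and 5.4.

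A reader might go further and infer that Arm 4 falls outside the Safety Population, because that definition and the TEAE definition refer to IP. The documents do not support building on this. Section 4.1 limits its definition of IP to its own section, and Section 8.1.9 has every safety summary shown by arm. It is a separate wording clarification and not part of this point.

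**Conclusion.** The point holds for the protocol as supplied. Following the stated rule gives a SOC column with about half the observation time of the other columns, and it is low relative to them if any first events start after EOT. The duration difference and the direction come from the documents. The size does not: about 4 points per affected Arm 1-3 patient is all that can be derived, and zero remains possible. The tables in the working rest on equal true 28-day risk, an assumed incidence and an assumed follow-up hazard.

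Two stronger readings are tempting. One is that SOC incidence will be roughly halved. That needs rare events and an equal hazard after treatment stops, and the protocol gives no basis for that or any other hazard. The other is that the safety evaluation as a whole is compromised. It is not, since the placebo-controlled comparison and the by-visit summaries are unaffected.

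Severity is minor to moderate. The unseen SAP could settle the matter.

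**What to change.** Add the following to Sections 8.1.9.2 and 8.1.9.3, or to the SAP before database lock.

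- **Common window.** For every cumulative adverse-event or medication table that includes Arm 4, count onset, worsening or use from the first dose of IP or SOC through the EOT visit, and no later than Day 29, in all arms. Day 29 is the upper limit of the Day 28 visit window.
- **No EOT visit.** Use one rule in all arms: cut off at the last attended visit on or before Day 29 and ignore data from later visits. Otherwise an Arm 1-3 patient who misses Day 28 but attends Day 56 would be credited to Day 29, while an Arm 4 patient last seen on Day 21 would stop there.
- **Later events.** Show events with onset after EOT, and the full table to Day 56, for Arms 1-3 only, clearly labelled.
- **Stated limits.** Say that early withdrawals still have shorter observation; under Section 3.3.4 they "should be encouraged to undergo the EOT safety and efficacy assessments at the time of withdrawal", which may be well before Day 28. Say also that an on-treatment onset first reported at Day 56 can be captured only in Arms 1-3.

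The cost is some wording and a second set of tables. Adverse-event dates are already recorded; medication dates need to be confirmed in the eCRF completion guidelines. No new visits or patients are needed. The drawback is that readers must not confuse the two sets of tables. The change removes the observation-time difference only, and the other limits on comparing with SOC remain.

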3.3.3. Premature Discontinuation of Investigational Product

Premature discontinuation of the IP by the Investigator is an important discussion that should include the Medical Monitor, if feasible, before the IP is discontinued.

Possible reasons for premature discontinuation from IP due to safety reasons include, but are not limited to, the following:

- Occurrence of an AE that, in the opinion of the Investigator, warrants the patient's permanent discontinuation from IP administration
- Hy's law criteria are met, defined by at least 3-fold elevations of ALT or AST above the ULN, elevation of serum total bilirubin to $>2 \times$ ULN without elevated serum alkaline phosphatase, and no other disease or condition can be found to explain the liver test abnormalities
- Known pregnancy or breastfeeding during the study drug administration period

Possible reasons for discontinuation from the IP *due to insufficient therapeutic effect* include, but are not limited to, clinical worsening or lack of clinical progress. If the Investigator deems the benefit-to-risk ratio of IP continuance acceptable, study drug administration of at least 48 h is encouraged before discontinuation from IP therapy for insufficient effect.

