5.1. Schedule of Assessments

The procedures to be performed throughout the study are outlined in the Schedule of Assessments ([Table 2](#)). A detailed description of each assessment may be found in [Section 5.2](#).

Table 2: Schedule of Assessments

Assessment ▼ Study Day ▶	Screening		Treatment													Follow-up	
	D -42 to -1	D -1	D1	Wk 1	D6	D7±1 ^a	Wk 2	D13	D14±1	Wk 3	D20	D21±1 ^a	Wk 4	D27	EOT ^b D28±1	D55	D56±2 ^c
In clinic visit	x		x			x			x			x			x		x
Informed consent	x																
Medical history	x																
Pulmonary function test	x																
CXR or CT scan ^d	x																
Height and weight ^e	x		x			x			x			x			x		
Physical examination ^f	x		x			x			x			x			x		x
Vital signs ^g	x		x			x			x			x			x		x
12-Lead ECG ^h	x		x						x						x		x
Pregnancy test (females) ⁱ	x		x														x
Urinalysis ^j	x		x			x			x			x			x		x
Blood for safety ^k	x		x			x			x			x			x		x
Blood samples for intense PK ^l			x			x			x			x			x		
Blood samples for sparse PK ^m			x			x			x			x			x		
Blood sample for biomarker ⁿ			x			x			x			x			x		
Patient-collected expectorated sputum ^o		x			x			x			x			x		x	
Induced sputum ^p	x		x			x			x			x			x		x
IP administration ^q			x	x	x	x	x	x	x	x	x	x	x	x	x		
██████████						█			█			█			█		
██████████			█			█			█			█			█		
█ ██████																	
Concomitant medication																	
Adverse events																	

Abbreviations: CT=computed tomography; CXR=chest radiograph; D=day; ECG=electrocardiogram; EOT=end of treatment; h=hour; IP=investigational product; min=minutes; PK=pharmacokinetics; PRO=patient-reported outcome; SOC=standard of care; Wk=week.

- a. As a last resort, with approval from the Sponsor, Days 7 and 21 may be home visits to allow for the collection of induced sputum and blood for PK and safety. Further details will be included in a separate plan.
- b. Patients in open-label SOC Treatment Arm 4 will be discontinued from the study after the EOT visit. For a patient who early terminates and agrees to complete the EOT visit, blood draws for PK will not be conducted. Women of child-bearing potential will have a pregnancy test at this visit.
- c. The follow-up visit will take place 28 days (± 2 days) after the EOT visit for double-blind Treatment Arms 1, 2, and 3.
- d. A CXR or CT scan will be done unless one that is less than 6 months old is available. If obtained at screening, eligibility will be confirmed prior to randomization.

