8.1.7. Demographic and Baseline Characteristics

Patient disposition, demographics, and baseline characteristics will be summarized using descriptive statistics for the Safety and micro-ITT Populations. No formal statistical analysis tests will be performed.

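### Does Section 8.1.9.2 need a separate output for adverse events that lead to stopping IP, as distinct from leaving the study?

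*Combined protocol and SAP*

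**What the plan says.** Section 8.1.9.2 (Adverse Events) names two outputs for AE-driven discontinuation. The by-arm one is that "AEs leading to study discontinuation will be summarized by treatment". The other is a listing: "A listing of patients who prematurely discontinue from the study due to AEs will be provided". Both refer to the study, not to the drug.

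Section 3.3.3 deals with stopping IP. The first safety reason it gives is an AE that, in the investigator's judgment, calls for the patient's "permanent discontinuation from IP administration". Section 3.3.4 deals with study withdrawal. Among its examples, the investigator may decide that the patient should "withdraw from the study protocol for reasons other than an adverse event (AE"), so that example leaves AEs out. The same section defines completion by the last visit. For Arm 4, "A patient will be considered to have completed the study when he or she completes the EOT visit"; for Arms 1 to 3 the last visit is the Day 56 follow-up.

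On reporting, Section 8.1.7 says: "Patient disposition, demographics, and baseline characteristics will be summarized using descriptive statistics for the Safety and micro-ITT Populations". Section 8 adds that summary tables are by arm, that everything reported or derived for a patient goes into listings, and that a detailed SAP will be finalized before database lock. Section 6 has the AE page of the eCRF record the action taken for each event.

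**The concern.** The protocol appears to separate two events and then to report only one of them. The only AE reason it names for an individual patient sits under stopping IP (3.3.3). The examples of study withdrawal (3.3.4) name no AE of the patient's own. A patient in Arms 1 to 3 who stops capsules for an AE and attends through Day 56 has, by 3.3.4, completed the study. Taken literally, that patient enters neither the by-arm summary nor the listing in 8.1.9.2.

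Section 2.2 makes safety and tolerability the secondary objective, and stopping treatment because of an AE is one of the most direct measures of tolerability. If such patients were numerous, the study-discontinuation row could be nearly empty while AE-driven treatment stops went uncounted by arm. TEAE tables by severity and relationship do not show who stopped. The exposure summary in 8.1.9.1 (doses taken, doses missed, compliance) does not show why.

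**Working it through.** The plan states no figure to reproduce, so this is mainly a comparison of texts.

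1. **Named outputs.** Section 8.1.9.2 names one summary and one listing for AEs leading to study discontinuation. It names none for AEs leading to IP discontinuation. The synopsis, Section 8.1.2 (secondary endpoints), Section 8.1.7 (disposition) and Section 8.1.9.1 (exposure) name none either. The literal observation is correct.

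2. **Does the affected patient exist under the plan?** The text allows a patient to be off IP but still in the study, but it never says so. Section 3.3.4 speaks of "Patients who wish to withdraw completely from this clinical study during the treatment period", which suggests that a lesser step is possible. Section 6.9 similarly removes a pregnant patient from treatment, without mention of the study. Against that, Table 2 has no off-treatment pathway. The unscheduled assessments that the plan describes are the EOT visit at withdrawal (footnote b: "For a patient who early terminates and agrees to complete the EOT visit") and a final evaluation requested of patients lost to follow-up. If patients who stop IP for an AE go through early termination in practice, the existing row and listing already capture them.

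3. **Is the wording strict?** It is not. Sections 3.1 and 5.1 describe Arm 4 patients as discontinued after EOT, while Section 3.3.4 says the same patients have completed the study. Section 4.6 refers to discontinuation for noncompliance without saying whether it means the drug or the study. The phrase in 8.1.9.2 may therefore be intended to cover stops under 3.3.3.

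4. **Is the information lost?** Action taken is collected for each AE (Section 6) and is listed under the general rule in Section 8. Disposition is tabulated by arm with a total column. Its rows are not described, so it may or may not show IP discontinuation by reason. The response options of the action-taken field are not shown either.

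5. **Size.** A blinded arm is 19 to 20 sparse-PK patients plus at least 6 intense-PK patients: 19 + 6 = 25 to 20 + 6 = 26. One patient is then 1/25 = 4.0 points or 1/26 = 3.8 points. This is the weight of any single patient in any table for that arm. Assuming 10 intense-PK patients per arm instead gives 29 to 30 per arm and 1/29 = 3.4 to 1/30 = 3.3 points. That assumption implies 72 + 3 × 10 = 102 patients, against the planned total of approximately 90 (72 + 18), so it carries no weight. The number of affected patients cannot be derived from the documents.

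**The case for a change.** The strongest case for a change is that it is cheap and the protocol's own structure points to it. Stopping IP and leaving the study have separate sections, completion is defined by a visit and not by dosing, and tolerability is a stated objective. One sentence, one table row and one listing would give a by-arm count that no named output provides, from a field already collected. Even if the wording in 8.1.9.2 is loose, it fits poorly with 3.3.3 and 3.3.4.

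The literal gap stands, and so does the relevance of the count to tolerability. What does not stand is the step from an unnamed output to a defect in the plan. Section 8 is a summary that defers detail to a later SAP, and nothing in 8.1.9.2 presents its outputs as exhaustive.

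The added row is also less simple than it looks. Permanent discontinuation of study treatment has no definition for Arm 4, a two- or three-drug regimen in which the rifamycin is optional and may be given for less than the full 28 days. Stopping one component could be counted or not. The TEAE definition in 8.1.9.2 is tied to IP, which Section 4.1 limits to SPR720 and placebo.

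**Conclusion.** No change to the plan is called for. The observation is accurate, but it concerns missing reporting detail that analysts can be expected to fill in the SAP, in the disposition table or from the AE listings. The planned row counts study discontinuation and counts it correctly, so no stated result or conclusion would be wrong. Safety analyses are descriptive, Section 8.1.4 plans no formal hypothesis, and the primary PK endpoints are not involved.

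No magnitude can be given beyond 4.0 to 3.8 points per hypothetical patient in a blinded arm at planned minimum enrolment, and the number of such patients may be zero. The conclusion rests on two assumptions that the text cannot confirm: that the action-taken field has a response for permanent discontinuation, and that the later SAP follows usual practice in tabulating it. Whoever writes that SAP may wish to say whether study discontinuation in 8.1.9.2 means the drug, the study or both. That is an optional clarification.
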